5.1.1.3 Other Risks with Cobimetinib

Rash

In the Phase III Study GO28141, combined rash events of all types and grades were reported more frequently in patients treated with cobimetinib plus vemurafenib than placebo plus vemurafenib (71.7% vs. 66.7%, respectively), although Grade ≥ 3 events (approximately 16% of patients) and types of rash reported were similar between study arms. Specific events in patients treated with cobimetinib plus vemurafenib included rash (39% all grades, 5.9% Grade ≥ 3 , 1.6% serious adverse events) and rash maculo-papular (14.6% all grades, 6.3% Grade ≥ 3 , 1.2% serious adverse events).

Generally, Grade ≥ 3 rash events were effectively managed with dose modification guidelines. In Study GO28141, approximately 90% of Grade ≥ 3 rash events resolved in both arms. Refer to [Appendix 3](#) for rash management guidelines.

Gastrointestinal Toxicity

A range of gastrointestinal adverse events, including nausea, vomiting, and diarrhea, have been reported in all cobimetinib studies in adult cancer patients.

In the Phase III Study GO28141, diarrhea was the most common adverse event reported. Diarrhea events of all severity grades were reported in 59.9% of patients and Grade 3 or 4 events were reported in 6.5% of patients treated with cobimetinib plus vemurafenib versus 30.9% (Grade 3) and 0.8% (Grade 4) in the patients treated with placebo plus vemurafenib. No Grade 5 events of diarrhea have been reported. Serious adverse events of diarrhea were reported in 1.2% of patients treated with cobimetinib plus vemurafenib.

Nausea and vomiting have been reported in association with cobimetinib. Most nausea and vomiting events were considered non-serious and low-severity grade. In the Phase III Study GO28141, nausea and vomiting events were reported more frequently in the active cobimetinib arm than the control arm (nausea 41.3% vs. 25.2%; vomiting 24.3% vs. 12.6%). However, of patients treated with cobimetinib plus vemurafenib, few experienced Grade 3 events (nausea 0.8%, vomiting 1.2%).

In the Phase I single-agent study (MEK4592g), all grades of nausea and vomiting were both reported as 33.9% with 0.9% reported for Grade ≥ 3 nausea and none reported for vomiting.

The combination of diarrhea, nausea, and vomiting has the potential to contribute to clinically significant volume depletion/dehydration from the combination of fluid losses with decreased oral intake. In the majority of cases, diarrhea has been effectively managed with antidiarrheal agents and supportive care. Routine antiemetic prophylaxis

is not recommended. Refer to [Appendix 3](#) for gastrointestinal toxicity management guidelines.

Hypersensitivity

There have been few reports of hypersensitivity and/or anaphylaxis in clinical trials with patients who have been exposed to cobimetinib monotherapy or cobimetinib when used with other agents. These have appeared to be isolated reports, and in some cases, occurred in patients with histories of drug allergies. Thus, the relationship of cobimetinib to these events is unclear.

In the Phase III Study GO28141, Grade 3 hypersensitivity events were reported in 3 patients in the cobimetinib and vemurafenib arm compared with no such events in the placebo plus vemurafenib arm. All events required hospitalization and treatment with steroids.

Investigators should promptly evaluate and treat patients who are suspected of experiencing a hypersensitivity reaction.

5.1.2 Risks Associated with Atezolizumab

Atezolizumab has been associated with risks such as IRRs and immune-related hepatitis, pneumonitis, colitis, pancreatitis, diabetes mellitus, hypothyroidism, hyperthyroidism, adrenal insufficiency, Guillain-Barré syndrome, myasthenic syndrome or myasthenia gravis, meningoencephalitis, *myocarditis*, and *hypophysitis*. In addition, systemic immune activation is a potential risk associated with atezolizumab. Refer to Section 6 of the Atezolizumab Investigator's Brochure for a detailed description of anticipated safety risks for atezolizumab and [Appendix 9](#).

Systemic immune activation is a rare condition characterized by an excessive immune response. Given the mechanism of action of atezolizumab, systemic immune activation is a potential risk when administered in combination with other immunomodulating agents. Systemic immune activation should be included in the differential diagnosis for patients who, in the absence of an alternative etiology, develop a sepsis-like syndrome after administration of atezolizumab, and the initial evaluation should include the following:

- CBC with peripheral smear
- PT, PTT, fibrinogen, and D-dimer
- Ferritin
- Triglycerides
- AST, ALT, and total bilirubin
- LDH
- Complete neurologic and abdominal examination (assess for hepatosplenomegaly)

If systemic immune activation is still suspected after the initial evaluation, contact the Medical Monitor for additional recommendations.

5.1.3 **Risks Associated with Regorafenib**

The overall safety profile of regorafenib is based on data from more than 1200 treated patients in clinical trials including placebo-controlled Phase III data for 500 patients with metastatic colorectal cancer and 132 patients with gastrointestinal stromal tumors. The most serious adverse drug reactions in patients who receive regorafenib are severe liver injury, hemorrhage, hypertension, dermatologic toxicity, cardiac ischemia and infarction, reversible posterior leukoencephalopathy, and gastrointestinal perforation. The most frequently observed adverse drug reactions ($\geq 30\%$) in patients who receive regorafenib are asthenia/fatigue, hand foot skin reaction, diarrhea, decreased appetite and food intake, hypertension, dysphonia and infection.

Please refer to the Stivarga (regorafenib) Prescribing Information for complete information regarding clinical safety.

5.1.4 **Management of Patients Who Experience Specific Adverse Events**

5.1.4.1 **Cobimetinib and Regorafenib Dose Modifications**

Cobimetinib and regorafenib dose modifications are provided in [Table 3](#).

Table 3 Recommended Cobimetinib and Regorafenib Dose Modifications

Grade (CTCAE) ^a	Recommended Cobimetinib Dose	Recommended Regorafenib Dose
Grade 1 or Grade 2 (tolerable)	No dose reduction. Maintain cobimetinib at the same dose of 60 mg QD (3 tablets)	No dose reduction. Maintain regorafenib at the same dose of 160 mg QD (4 tablets)
Grade 2 (intolerable) or Grade 3 or 4 (any)		
First appearance	Interrupt treatment until Grade ≤ 1 , restart treatment at 40 mg QD (2 tablets)	Interrupt treatment until Grade ≤ 1 , restart treatment at 120 mg QD (3 tablets)
Second appearance	Interrupt treatment until Grade ≤ 1 , restart treatment at 20 mg QD (1 tablet)	Interrupt treatment until Grade ≤ 1 , restart treatment at 80 mg QD (2 tablets)

Grade (CTCAE) ^a	Recommended Cobimetinib Dose	Recommended Regorafenib Dose
Third appearance	Consider permanent discontinuation	Consider permanent discontinuation

CTCAE = Common Terminology Criteria for Adverse Events; NCI = National Cancer Institute; QD = once daily.

^a The intensity of clinical adverse events graded by NCI CTCAE v4.0.

5.1.4.2 Atezolizumab Dose Modifications

There will be no dose reduction for atezolizumab in this study.

Guidelines for management of general adverse events are outlined in [Table 4](#).

Table 4 Guidelines for Management of Patients Who Experience Adverse Events in Arm A and Arm B

Event	Action to Be Taken
Other toxicities: Grade 1	No action required.
Other toxicities: Grade 2	No action required
Other toxicities: Grade 3 or 4	
Interrupt dosing of atezolizumab (or cobimetinib if in Arm A) depending on the attribution of the toxicity, at the discretion of the investigator. During this time, treatment may continue with the other non-attributable treatment agent (i.e., either the atezolizumab in arm A or B or cobimetinib if in Arm A).
 
If AE resolves to Grade ≤ 1 within 1 cycle, then restart dosing of the attributable drug (atezolizumab at fixed dose and cobimetinib decreased by 1 dose level).
 
If the AE does not resolve to Grade ≤ 1 within 1 cycle, permanently discontinue the attributable drug. If one drug is discontinued dosing of the other drug may continue at the discretion of the investigator.
 
If the Grade 4 AE recurs (a second time), the attributable drug should be discontinued. If one drug is discontinued dosing of the other drug may continue at the discretion of the investigator.
 
For Grade ≥ 3 toxicities associated primarily with laboratory abnormalities only, study treatment may continue without interruption and/or dose reduction at the discretion of the investigator per institutional practice.

AE = adverse event.

Additional guidelines for specific adverse events delineated by the different study arms are provided in the subsections below and the specific management guidelines are highlighted in [Appendix 3](#) for cobimetinib plus atezolizumab. For information regarding

management of atezolizumab-associated adverse events, please refer to the [Appendix 9](#).

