4.3.2 Dosage, Administration, and Compliance

4.3.2.1 Cobimetinib

Patients randomized to cobimetinib will receive 60 mg (three tablets of 20 mg each) orally once daily for Days 1–21 of a 28-day cycle as stated in Section 3.1, including Figure 2. This 4-week period is considered a treatment cycle.

Cobimetinib should be taken at the same time every day. It can be taken with or without food. If a dose of cobimetinib is missed or if vomiting occurs when the dose is taken, resume dosing with the next scheduled dose.

Guidelines for dosage modification and treatment interruption or discontinuation are provided in Section 5.1.4.

Any overdose or incorrect administration of study drug should be noted on the Study Drug Administration electronic Case Report Form (eCRF). Adverse events associated with an overdose or incorrect administration of study drug should be recorded on the Adverse Event eCRF (See Section 5.3).

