4.6.2 Study Treatment Discontinuation

Patients must discontinue study treatment if they experience any of the following:

- Disease progression (see Section 4.3.2.4 for dosing beyond progression)
- Symptomatic deterioration attributed to disease progression as determined by the investigator after integrated assessment of radiographic data, biopsy results, and clinical status
- Intolerable toxicity related to any study drug
- Any medical condition that may jeopardize the patient's safety if he or she continues study treatment
- Use of another non-protocol anti-cancer therapy (see Section 4.4.2)
- Pregnancy

Patients must provide written consent to acknowledge deferring any standard treatment options that may exist in favor of continuing treatment at the time of initial progression.

The primary reason for study drug discontinuation should be documented on the appropriate eCRF.

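### For cobimetinib toxicity outside Appendix 3, Tables 3 and 4 give incompatible instructions when the same Grade 4 event recurs, and no text ranks them

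*Protocol*

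**What the plan says.** Protocol Section 4.3.2.1, on cobimetinib dosing, directs the reader to Section 5.1.4 as a whole: "Guidelines for dosage modification and treatment interruption or discontinuation are provided in Section 5.1.4". Two tables there apply to cobimetinib in Arm A.

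- **Table 3 (Section 5.1.4.1)** is organised by drug, for cobimetinib and regorafenib. One ladder covers "Grade 2 (intolerable) or Grade 3 or 4 (any" events. At the first appearance, interrupt and restart at 40 mg. At the second, interrupt until Grade 1 or better, then "restart treatment at 20 mg QD (1 tablet". At the third, "Consider permanent discontinuation".
- **Table 4 (Section 5.1.4.2)** is titled for Arms A and B. After a Grade 3 or 4 event that resolves to Grade 1 or better within one cycle, the attributable drug restarts, with cobimetinib one dose level lower. Then: "If the Grade 4 AE recurs (a second time), the attributable drug should be discontinued". For Grade 3 or higher events there is an exception at the investigator's discretion: for "toxicities associated primarily with laboratory abnormalities only, study treatment may continue without interruption and/or dose reduction".

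Section 5.1.4.3 sends a list of named Arm A toxicities to Appendix 3, which has its own rules for them. Section 4.6.2 requires study treatment to stop for "Intolerable toxicity related to any study drug". The introduction to Section 5 tells readers to use each arm's own guidelines.

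**The concern.** Both tables reach the same patient. Table 4 stands under an atezolizumab heading, but its title covers Arm A and its text names cobimetinib as a drug that may be interrupted, reduced or stopped. Table 3's cobimetinib column can only concern Arm A, since no other arm is assigned cobimetinib.

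If a Grade 4 event attributed to cobimetinib resolves and then returns, one table restarts the drug at 20 mg and the other ends it. Whether to rechallenge would then depend on which table the site consulted, in a study of about 75 centers (Section 9.4). Section 5.3.3, Table 7, which grades events not listed in the CTCAE, reserves Grade 4 for life-threatening events or those needing urgent intervention. What is at stake is a patient-safety instruction and its uniform application.

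**Working it through.** **Comparing the tables.** The plan states no figure to reproduce here. Take a Grade 4 event attributed to cobimetinib in Arm A, of a type Appendix 3 does not cover, that resolves to Grade 1 or better within one cycle.

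| Occurrence of the same Grade 4 event | Table 3 | Table 4 | Compatible? |
|---|---|---|---|
| First | Restart at 40 mg | Restart one level lower (40 mg) | Yes |
| Second, reading Table 4's recurrence as the second occurrence | Restart at 20 mg | Discontinue | No |
| Third, reading Table 4's recurrence as the second recurrence | Consider discontinuation | Should discontinue | Differ in strength only |

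The second row is the plain reading. On either reading the tables differ. If the event is primarily a laboratory abnormality, Table 4 lets the investigator continue without change, so the clash bears mainly on clinical events.

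**How many patients could come near this.** The only Grade 4 rate for cobimetinib alone is in Protocol Section 1.5.2 (single-agent study, 115 treated, all dose levels including 80, 100 and 125 mg).

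1. Grade 4 rate: 5/115 = 4.35%; exact (Clopper-Pearson) 95% CI 1.43% to 9.85%.
2. Applied to about 180 Arm A patients: 180 × 4.35% = 7.8; range 180 × 1.43% = 2.6 to 180 × 9.85% = 17.7.
3. Share outside Appendix 3. The five most frequent Grade 3 and 4 terms, converted to counts out of 115, are hyponatremia 11 (9.6%), fatigue 10 (8.7%), anemia 9 (7.8%), diarrhea 7 (6.1%) and hypokalemia 7 (6.1%), a total of 44 patient-events. Of these only diarrhea has an Appendix 3 rule.
   - Not diarrhea: 37/44 = 84.1%.
   - Not diarrhea and not a laboratory finding (fatigue only): 10/44 = 22.7%.
4. Patients with one such Grade 4 event:
   - laboratory findings excluded: 7.8 × 22.7% = 1.8 (0.6 to 4.0);
   - laboratory findings included: 7.8 × 84.1% = 6.6 (2.2 to 14.9).

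So roughly 2 to 7 of 180 patients would have a first qualifying event. The conflict further requires attribution to cobimetinib, resolution within one cycle, and recurrence of the same event at Grade 4. The documents give no rate for any of these, so the number affected is smaller and may be zero.

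**The case against.** The strongest reply is that the protocol already points to Table 4. Section 5 directs readers to arm-specific guidelines, and Table 4 is the one titled by arm. Its rows are for other toxicities, which is the residual class at issue. It has a specific rule for recurrent Grade 4 events, whereas Table 3 pools intolerable Grade 2 with Grades 3 and 4 and labels its doses as recommended. Section 4.6.2 is mandatory, and a Grade 4 event returning on a reduced dose is a natural case of intolerable toxicity. All of this leans toward stopping, and a careful investigator would probably stop. But it is inference: the arm-specific pointer names no table, Table 4 is itself a guideline, and Section 4.6.2 does not say when toxicity becomes intolerable. Table 3 still directs a restart in writing.

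Three stronger readings are tempting but unsupported.

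- A reader might infer a conflict at any second Grade 4 event. Table 4 speaks of the Grade 4 event recurring, that is, the same event. A different Grade 4 event does not trigger its discontinuation sentence.
- A reader might infer that the row "Other toxicities: Grade 2", which requires no action, contradicts Table 3 on intolerable Grade 2. It is a looser instruction, but it does not forbid Table 3's interruption and reduction, and Section 4.6.2 covers intolerable toxicity.
- A reader might take 2 to 7 as the number of patients affected. The shares use only the five most frequent terms, dropping all rarer ones, including types that Appendix 3 covers. The mix is mostly Grade 3 (53 patients with Grade 3 against 5 with Grade 4), and no Grade 4 fatigue event is documented. The counts are at best a loose upper bound.

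**Conclusion.** The inconsistency is real but narrow. It applies to a cobimetinib-attributed toxicity in Arm A with no Appendix 3 rule, when the same Grade 4 event recurs after resolving within one cycle. On the plain reading the two instructions are incompatible; on the other reading they differ only in force. Surrounding text favours Table 4 without saying that it governs.

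The effect is small: few patients, possibly none. The rough counts assume that the single-agent Grade 4 rate carries over to the combination (where it may be higher) and that the mix of common Grade 3 and 4 terms holds for Grade 4. Nothing here bears on overall survival, alpha or power. The change is worth making because it removes two conflicting safety instructions at almost no cost.

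**What to change.** Make two wording edits in the next amendment.

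1. Under Table 3 add: *Where Appendix 3 gives a rule for the toxicity, Appendix 3 governs. For other toxicities in Arm A, if the same Grade 4 event attributed to cobimetinib recurs, Table 4 governs and cobimetinib is discontinued; Table 4's laboratory-only exception still applies.*
2. In Table 4, reword the condition on recurrence to: *If the same Grade 4 AE occurs a second time.*

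The word *same* matters. Without it the edit would create a new, stricter rule stopping cobimetinib after two unrelated Grade 4 events. The first sentence keeps Appendix 3's own rules intact, including those that allow cobimetinib to restart after serous retinopathy, Grade 4 CPK elevation or Grade 2 pneumonitis.

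As optional tidying, the Grade 2 row of Table 4 could refer intolerable Grade 2 events attributed to cobimetinib to Table 3.

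The cost is a few lines of text. Data collection, sample size and analysis do not change.

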5.1.4.3 Management of Cobimetinib- and Atezolizumab-Specific Adverse Events (Arm A)

Toxicities associated or possibly associated with cobimetinib plus atezolizumab treatment should be managed according to standard medical practice.

Refer to [Appendix 3](#) for management of cobimetinib plus atezolizumab specific toxicities, including gastrointestinal toxicity, hepatotoxicity, dermatologic toxicity, pulmonary toxicity, potential eye toxicity, left ventricular ejection fraction, rhabdomyolysis and elevated CPK, hemorrhage, and systemic immune activation.

Guidelines for management of patients who experience atezolizumab-associated adverse events, including infusion-related reactions and immune-related events (e.g., endocrine, ocular, pancreatic, and neurologic events), are provided in [Appendix 9](#).

5.1.4.4 Management of Adverse Events in the Atezolizumab Monotherapy Arm (Arm B)

Guidelines for management of patients who experience specific adverse events associated with atezolizumab, including infusion-related reactions and immune-related events (e.g., pulmonary, hepatic, gastrointestinal, endocrine, ocular, pancreatic, dermatologic, and neurologic events), are provided in [Appendix 9](#).

5.1.4.5 Management of Regorafenib–Associated Adverse Events (Arm C)

Toxicities associated or possibly associated with regorafenib treatment should be managed according to standard medical practice. Highlighted below are the dose modifications for selected adverse events outlined in the Stivarga (regorafenib) prescribing information. Please refer to the Stivarga (regorafenib) prescribing information for further guidance.

For symptomatic Grade 2 hypertension interrupt regorafenib and reduce the dose of regorafenib by a dose level.

Recommended dose modifications for hand-foot skin reaction and palmar-plantar erythrodysesthesia syndrome are provided in [Table 5](#), and recommended dose modifications for liver function abnormalities are provided in [Table 6](#).

Table 5 Recommended Dose Modification and Measure for Hand–Foot Skin Reaction/Palmar-Plantar Erythrodysesthesia Syndrome

Skin Toxicity Grade	Occurrence	Recommended Dose Modification and Measures
Grade 1	Any	Maintain dose level and immediately institute supportive measures for symptomatic relief
Grade 2	First occurrence	Decrease dose by 40 mg and immediately institute supportive measures. If no improvement occurs despite dose reduction, interrupt therapy for a minimum of 7 days, until toxicity resolves to Grade 0–1. A dose re-escalation is permitted at the discretion of the physician.
	No improvement within 7 days or second occurrence	Interrupt therapy until toxicity resolves to Grade 0–1. When restarting treatment, decrease dose by 40 mg. A dose re-escalation is permitted at the discretion of the physician
	Third occurrence	Interrupt therapy until toxicity resolves to Grade 0–1. When restarting treatment, decrease dose by 40 mg. A dose re-escalation is permitted at the discretion of the physician.
	Fourth occurrence	Discontinue treatment with regorafenib permanently.
Grade 3	First occurrence	Institute supportive measure immediately. Interrupt therapy for a minimum of 7 days until toxicity resolves to Grade 0–1. When restarting treatment, decrease dose by 40 mg. A dose re-escalation is permitted at the discretion of the physician.
	Second occurrence	Institute supportive measures immediately. Interrupt therapy for a minimum of 7 days until toxicity resolves to Grade 0–1. When restarting treatment, decrease dose by 40 mg.
	Third occurrence	Discontinue treatment with regorafenib permanently.

Table 6 Recommended Measures and Dose Modifications in Case of Drug-Related Liver Function Test Abnormalities

Observed elevations of ALT and/or AST	Occurrence	Recommended measures and dose modification
$\leq 5 \times \text{ULN}$ (maximum Grade 2)	Any occurrence	Continue regorafenib treatment. Monitor liver function weekly until transaminases return to $< 3 \times \text{ULN}$ (Grade 1) or baseline
$> 5 \times \text{ULN}$ $< 20 \times \text{ULN}$ (Grade 3)	First occurrence	Interrupt regorafenib treatment. Monitor transaminases weekly until return to $< 3 \times \text{ULN}$ or baseline. Restart: If the potential benefit outweighs the risk of hepatotoxicity, restart regorafenib treatment, reduce dose by 40 mg, and monitor liver function weekly for at least 4 weeks.
	Re-occurrence	Discontinue treatment with regorafenib permanently.
$> 20 \times \text{ULN}$ (Grade 4)	Any occurrence	Discontinue treatment with regorafenib permanently.
$> 3 \times \text{ULN}$ (Grade 2 or higher) with concurrent bilirubin $> 2 \times \text{ULN}$	Any occurrence	Discontinue treatment with regorafenib permanently. Monitor liver function weekly until resolution or return to baseline. Exception: patients with Gilbert's syndrome who develop elevated transaminases should be managed as per the above outlined recommendations for the respective observed elevation of ALT and/or AST.

ULN = upper limit of normal.

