4.3.2.3 Regorafenib

Regorafenib will be used in the commercially available formulation.

Patients randomized to regorafenib (Arm C), will receive regorafenib at the approved dose level of 160 mg (four tablets of 40 mg each) orally once daily on Days 1–21 of a 28-day cycle (see Section 3.3 and Figure 2 in Section 3.1). This 4-week period is considered a treatment cycle.

Regorafenib should be taken at the same time each day. The tablets should be swallowed whole with water after a light meal that contains <30% fat. An example of a light (low-fat) meal would include one portion of cereal (about 30 g), one glass of skimmed milk, one slice of toast with jam, one glass of apple juice, and one cup of coffee or tea (520 calories, 2 g fat).

The study investigator may implement dose interruption or dose reduction in response to adverse events to ensure patient safety and tolerability. Guidelines for dosage modification and treatment interruption or discontinuation are provided in Section 5.1.4.1. Please refer to the Stivarga (regorafenib) prescribing information for more details.

Any overdose or incorrect administration of regorafenib should be noted on the Regorafenib Administration eCRF. Adverse events associated with an overdose or incorrect administration of regorafenib should be recorded on the Adverse Event eCRF (See Section 5.3).

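### For regorafenib (Arm C), Table 3 is inconsistent with Tables 5 and 6 on some hand-foot skin and liver-test events, and the protocol does not expressly say which table governs

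*Protocol*

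**What the plan says.** Protocol Section 4.3.2.3 starts Arm C at the "approved dose level of 160 mg (four tablets of 40 mg each") and then tells sites: "Guidelines for dosage modification and treatment interruption or discontinuation are provided in Section 5.1.4.1". It adds a pointer to the regorafenib prescribing information. It does not mention Section 5.1.4.5.

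Section 5.1.4.1 holds Table 3, which has a regorafenib column. For Grade 1 or tolerable Grade 2 events the instruction is "Maintain regorafenib at the same dose of 160 mg QD (4 tablets"). The action rows cover "Grade 2 (intolerable) or Grade 3 or 4 (any"). At the first appearance treatment is interrupted until Grade 1 or better, then "restart treatment at 120 mg QD (3 tablets"). At the second, "restart treatment at 80 mg QD (2 tablets"). At the third, the site is asked to consider stopping permanently. A footnote to the grade column says that the grading is of the intensity of clinical adverse events.

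Section 5.1.4.5 holds Tables 5 and 6, presented as modifications for selected events drawn from the prescribing information.

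- **Table 5 (hand-foot skin reaction):** at the first Grade 2 occurrence, "Decrease dose by 40 mg and immediately institute supportive measures", with no split by tolerability. Further 40 mg reductions follow an interruption, and stopping comes at the fourth Grade 2 occurrence. Re-escalation is allowed at the physician's discretion in every Grade 2 row that carries a reduction.
- **Table 6 (liver tests):** for a recurrent Grade 3 or any Grade 4 ALT/AST elevation, "Discontinue treatment with regorafenib permanently".

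**The concern.** A site managing one Arm C patient can find two written instructions for the same event. Section 4.3.2.3, where a site would start, names only the section with the general ladder. Arm C has about 90 patients and is the reference in both primary overall survival comparisons (Protocol Section 6.4.1; SAP Section 4.4.1). The trial is open-label, so these dosing decisions are made knowing the arm.

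Two things are at stake. One is patient safety: restart and permanent stop are opposite instructions for a Grade 4 transaminase elevation, and Section 5.1.3 names severe liver injury first among the most serious regorafenib reactions. The other is interpretability. The SAP summarises dose intensity by arm (Section 4.6.1) and major protocol deviations (Section 4.2). Where two instructions conflict, it is unclear what counts as following the protocol.

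**Working it through.** **Inputs.** Starting dose 160 mg as four 40 mg tablets, Days 1–21 of 28 (Section 4.3.2.3); Table 3 (Section 5.1.4.1); Tables 5 and 6 (Section 5.1.4.5).

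**Reproducing Table 3.** One tablet fewer: 160 − 40 = 120 mg. Two fewer: 160 − 2 × 40 = 80 mg. Both match its stated restart doses, so its lowest level is 80 mg.

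**Walking Table 5 for Grade 2, without re-escalation.** First occurrence 160 − 40 = 120 mg; second 120 − 40 = 80 mg; third 80 − 40 = 40 mg; fourth, stop.

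**Where the tables differ.**

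| Event | Table 3 | Table 5 or 6 |
|---|---|---|
| (1) First Grade 2 hand-foot reaction, tolerable | 160 mg | 120 mg (Table 5) |
| (2) Third Grade 2 hand-foot occurrence (intolerable, for Table 3) | consider stopping | interrupt, restart 40 mg lower: 40 mg without re-escalation (Table 5) |
| (3) First Grade 4 ALT/AST | restart at 120 mg, read literally | stop permanently (Table 6) |
| (4) Second Grade 3 ALT/AST | restart at 80 mg, read literally | stop permanently (Table 6) |

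For row (1) the gap is 40/160 = 25% of the daily dose. Over a full 21-day course that is 160 × 21 = 3360 mg against 120 × 21 = 2520 mg.

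**Where they agree on dose.** First Grade 3 hand-foot reaction (120 mg in both), second Grade 3 hand-foot reaction (80 mg in both), and first Grade 3 ALT/AST if treatment is restarted (120 mg in both). A first intolerable Grade 2 hand-foot reaction reaches 120 mg under both tables; Table 3 interrupts first and Table 5 does not.

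**Searching for a precedence rule.**

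- The introduction to Section 5 says that guidelines are separate by arm and directs sites to those for each arm.
- Section 5.1.4.2 describes the later arm-specific subsections as additional guidance.
- Section 5.1.4.5 does not say that its tables replace Table 3. It also asks for a reduction by one dose level for symptomatic Grade 2 hypertension, and only Table 3 lays regorafenib levels out, so the two sections have to be read together.

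None of these says which table prevails.

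**The case against.** The strongest reply is that a specific table normally overrides a general one. Section 5 points sites to their arm's guidelines, Section 5.1.4.5 is labelled for Arm C, and Section 4.3.2.3 also refers to the prescribing information, the stated source of Tables 5 and 6. Many investigators would read it so. This makes it plausible that Tables 5 and 6 govern, but it is not a stated rule: Table 3's regorafenib column is itself Arm C guidance.

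On rows (3) and (4), Table 3's footnote speaks of clinical adverse events, and transaminase elevations are laboratory findings with their own table. That reading is natural, and it makes these two rows less certain than the first two. But the action rows say "Grade 2 (intolerable) or Grade 3 or 4 (any") and nothing expressly excludes laboratory events.

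On row (2), being asked to consider stopping does not forbid continuing, so this is partly a gap in Table 3's ladder. Re-escalation also means that 40 mg is not a fixed destination. Both points stand. All three tables are titled as recommendations, which also softens the conflict.

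Stronger readings are tempting, but the documents do not support them:

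- **A path to 0 mg.** A reader might count failure to improve within 7 days and a second occurrence as separate reductions, giving 160 − 4 × 40 = 0 by the third occurrence. Table 5 puts them in one row, joined by an or, with one reduction.
- **A count of affected patients.** Section 5.1.3 lists hand-foot skin reaction among reactions seen in at least 30% of patients, and 0.30 × 90 = 27. That figure is for any grade, no grade split is given, and Grade 3 events largely agree between the tables.
- **Comparator dose intensity or survival already compromised.** No event rates by grade or site practices are given from which such an effect could be shown.

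**Conclusion.** The inconsistency is real and limited. It concerns two event types, hand-foot skin reaction and liver-test elevation, and four situations within them. Row (1) is a direct contradiction of 40 mg a day. Row (2) leads to a dose level that Table 3 does not contain, assuming no re-escalation. Rows (3) and (4) are opposite instructions if Table 3 is read literally; they disappear if its footnote is meant to exclude laboratory events, which the protocol does not say.

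The number of patients affected, and any effect on Arm C dose intensity or overall survival, cannot be derived from the documents. The planned sample size and power do not depend on the point. It merits correction because it touches patient safety and the dosing rules of the comparator, and because the repair is cheap.

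**What to change.** Reconcile Section 4.3.2.3, Table 3, Table 5 and Table 6 in an amendment:

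- State which table governs hand-foot skin reaction and which governs liver-test events.
- State whether Table 3 applies to laboratory abnormalities.
- Reconcile the dose levels reached in Table 3 with those reached in Table 5.
- Add Section 5.1.4.5 to the cross-reference in Section 4.3.2.3.

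The sponsor's clinicians decide which instruction stands in each case; this review takes no view on that. The cost is table wording, one cross-reference and a memo to sites, with no extra patients, visits or data.
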